## Protocol Revision History

Version Number: 1.0

Version Date: 12/16/2014

Summary of Revisions Made: Initial protocol approved by NCCAM (NCCIH)

Version Number: 2.1

Version Date: 01/20/2015

Summary of Revisions Made: Change stretching/strengthening to physical conditioning; physical mobility assessment moved to baseline, medication inventory added to Week 8, Credibility and Expectations of Treatment moved to randomization, NCCAM changed to NCCIH

Version Number: 2.2

Version Date: 07/15/2016

Summary of Revisions Made: Increased sample size to 60 participants and updated staff contact address.

Version Number: 2.3

Version Date: 09/28/2016

Summary of Revisions Made: Increased sample size to 90 participants and updated staffing.

## PRÉCIS

### **Study Title**

Lessening Incontinence through Low-impact Activity (LILA), a.k.a. Yoga to Enhance Behavioral Self-Management of Urinary Incontinence in Women

### **Objectives**

To develop and test procedures for a future full-scale efficacy trial of a group-based yoga therapy intervention in middle-aged and older women with urinary incontinence.

### **Design**

Pilot, randomized, parallel-group trial of a group-based yoga therapy program versus physical conditioning control program for treatment of urinary incontinence in ambulatory middle-aged and older women.

### **Sample Size and Population**

Up to ninety women aged 50 years and older who document stress-, urgency-, or mixed-type incontinence occurring an average of once per day on a voiding diary, are not participating in other organized yoga activities, are not using other clinical treatments for incontinence, and meet minimum mobility and other eligibility criteria will be recruited from the general San Francisco Bay Area.

### **Interventions and Duration**

Eligible women will be randomized in a 1:1 ratio to participate in either a 12-week yoga therapy program (N~45) or a time-equivalent physical conditioning exercise control program (N~45). Women randomized in the yoga therapy program will take part in twice weekly group yoga classes focusing on selected Iyengar-based yoga techniques as well as practice study-specific yoga techniques at home for at least one hour per week for a total of 12 weeks. Women randomized to the physical conditioning control group will take part in twice weekly group physical conditioning classes and practice physical conditioning exercises at least one hour per week at home for 12 weeks.

### **Outcomes and Measurements**

To assess feasibility, rates of enrollment and retention will be carefully monitored, and adherence yoga or stretching practice will be assessed during the 12-week intervention as well as 12 weeks after the end of the intervention programs. To collect preliminary data on treatment efficacy for urinary incontinence, validated 3-day voiding diaries will be used to document changes in the frequency of incontinence over 12 weeks of treatment, as well as persistence of changes 12 weeks after the end of the intervention programs. To collect preliminary data on treatment efficacy for other symptom and quality-of-life outcomes, validated self-administered questionnaires will also be used to examine changes in other urinary tract symptoms, condition-specific quality of life, and anxiety and perceived stress over 12 weeks of treatment, as well as persistence of changes 12 weeks after the end of the intervention programs.

## 1. STUDY OBJECTIVES

**Aim 1: To examine the feasibility of recruiting and retaining ambulatory women aged 50 years and older into a randomized trial of a yoga therapy versus physical conditioning program for treatment of incontinence, and explore potential differences in retention and adherence by duration of treatment and follow-up.**

Expected outcome 1: We expect to recruit and randomize 15 to 30 women in each 3-month enrollment wave to confirm our ability to assemble a class size of 8 to 15 women per group per wave in a future full-scale trial.

Expected outcome 2: We expect drop-out rates in both treatment groups to increase over time, but remain <20% after 12 weeks of treatment and <30% at 12 weeks of post-treatment follow-up.

Expected outcome 3: We expect adherence to decrease over time, but remain >75% at 12 weeks of treatment (for group classes and home practice) and >50% at 12 weeks post-treatment (for home practice only).

**Aim 2: Explore whether a clinically meaningful reduction in incontinence frequency could be detected in a full-scale trial of yoga versus physical conditioning, and examine potential differences in treatment efficacy by duration of treatment and follow-up.**

Expected outcome 1: We will collect data on the standard deviation, intra-class correlation, and between-group difference in change in incontinence frequency to guide sample size projections for a future full-scale trial powered to detect a 25% greater reduction in incontinence frequency associated with yoga therapy.

Expected outcome 2: We will examine time-related trends in treatment effects on incontinence frequency to guide expectations of treatment efficacy over 8 versus 12 weeks of treatment as well as persistence of treatment benefits after 12 weeks of post-treatment follow-up in a future full-scale trial.

**Aim 3: Explore potential effects of yoga versus physical conditioning on other symptom and quality-of-life outcomes associated with incontinence and examine potential differences in treatment efficacy by duration of treatment and follow-up.**

Expected outcome 1: We will collect data on standard deviations, intra-class correlations, and between-group differences for changes in anxiety, depression, and quality-of-life questionnaire scores to guide estimates of minimum detectable effects for these secondary outcomes in a future full-scale trial.

Expected outcome 2: We will examine time-related trends in treatment effects on these secondary outcomes to guide expectations of treatment efficacy over 8 versus 12 weeks as well as persistence of benefits after 12 weeks of post-treatment follow-up in a future full-scale trial.

## 2. BACKGROUND AND RATIONALE

### 2.1 Background on Condition

Approximately one in four middle-aged and older women suffer from urinary incontinence, a condition associated with depression, social isolation, functional decline, falls and fractures, and admission to long-term care facilities. In economic analyses, the annual estimated direct costs of incontinence among U.S. women exceed \$20 billion, greater than that of breast, ovarian, cervical, and uterine cancers combined.

Current first-line treatment for both stress- and urgency-type incontinence includes behavioral management strategies such as bladder re-training and pelvic floor exercises to increase bladder capacity, strengthen the muscles supporting the bladder neck, and suppress involuntary bladder contractions. Unfortunately, many patients who attempt to practice these techniques after routine teaching by general practitioners are not able to do so effectively. Although the efficacy of these techniques can be improved by in-depth, one-on-one training and biofeedback with pelvic physical therapists or other specialized medical practitioners, this type of intensive pelvic floor rehabilitation therapy is costly, and access to trained pelvic physical therapists in the community is limited.

Second-line treatment for urgency-type incontinence (i.e., leakage caused by a sudden urge to void) consists primarily of anticholinergic drugs that are modestly effective in reducing incontinence, but have multiple side effects such as dry mouth, stomach upset, constipation, and cognitive impairment. As a result, over half of patients who initiate anticholinergic therapy discontinue it within a year. For stress-type incontinence (i.e., leakage with activities that increase abdominal pressure), surgery and other invasive procedures can be effective, but are inappropriate or poorly tolerated by many patients, especially older women who are at greatest risk of incontinence. There is a need for alternate therapies that are not only effective, but also more accessible and better tolerated.

## 2.2 Study Rationale

Yoga is a complementary behavioral intervention with the potential to improve incontinence through multiple mechanisms, while avoiding the shortcomings of existing therapies. When taught in a way that emphasizes mindful awareness of specific bodily structures, yoga can be used to help women control and strengthen their pelvic floor muscles through group instruction and home practice. As a result, a group-based yoga program that incorporates practice of specific yoga postures to promote awareness and engagement of the pelvic floor may provide a more accessible alternative to traditional, one-on-one pelvic floor rehabilitation therapy, provided that it can be taught in a standardized way that is appropriate for patients' clinical and safety needs.

Yoga can also alleviate anxiety, stress, and associated autonomic imbalance, as factors that contribute to incontinence and magnify its impact on quality of life. Clinical studies indicate that women with high self-reported levels anxiety or stress are at increased risk of developing incontinence, and that women with chronic incontinence experience worsening of their incontinence after exposure to stress-inciting events. Although cognitive behavioral therapy, hypnotherapy, and other types of psychotherapy have been explored as potential treatments for incontinence, these strategies are again limited by the need for intensive, one-on-one sessions with mental health specialists. In contrast, a group-based yoga program that promotes relaxation through deep breathing and other restorative techniques may provide a more generalizable, community-based strategy for women to decrease anxiety and stress in order to improve both bladder control and quality of life.

To examine the feasibility of using yoga to treat incontinence in middle-aged and older women, our research team previously developed a group-based, Iyengar-style yoga therapy program consisting of twice weekly classes and once weekly home practice sessions. In a pilot trial involving 19 ambulatory middle-aged and older women with at least 7 episodes of urgency, stress, or mixed-type incontinence per week, women

randomized to this therapeutic yoga program experienced a 70% decrease in incontinence frequency over 6 weeks, versus 16% for the waitlist control (P=.05), without any increase in adverse events.

We now plan to conduct an R34-scale pilot study to develop, test, and refine procedures for a more rigorous, full-scale efficacy trial of yoga for treatment of incontinence in middle-aged and older women. Information collected during this pilot trial will allow the research team to evaluate and strengthen procedures for recruiting, randomizing, and retaining participants for a future efficacy trial, as well as collect more preliminary data on the potential efficacy of the study interventions on clinical and quality-of-life outcomes.

### **3. STUDY DESIGN**

The LILA study is a pilot randomized parallel-group trial of a group-based yoga therapy program versus physical conditioning control program for treatment of urinary incontinence in ambulatory middle-aged and older women. Women aged 50 years and older who document at least 3 episodes of stress-, urgency-, or mixed-type incontinence on a screening 3-day voiding diary, are not using other clinical treatments for incontinence, and meet minimum physical mobility requirements and other eligibility criteria will be recruited from the general San Francisco Bay Area by research coordinators based at the University of California San Francisco. Eligible women will be randomized in a 1:1 ratio to participate in either a 12-week yoga therapy program (N~45) focusing on selected Iyengar-based yoga techniques, or a time-equivalent physical conditioning exercise control program (N~45). Women randomized in the yoga therapy program will take part in twice weekly group yoga classes involving 8 to 15 other women as well as practice study-specific yoga techniques at home for at least one hour per week for a total of 12 weeks. Women randomized to the physical conditioning control group will take part in twice weekly group physical conditioning classes and practice physical conditioning exercises at least one hour per week at home for 12 weeks. During a 12-week post-treatment follow-up period, participants will also be encouraged to continue practicing yoga or stretching exercises for at least an hour per week.

To address aim 1, the study team will carefully track the progress of recruitment and randomization and monitor participants' adherence to group classes and home practice over 12 weeks of yoga or stretching training as well as 12 weeks after the end of the training programs. To address aim 2, validated voiding diaries will be used to document changes in the frequency of urinary incontinence over 12 weeks of yoga or stretching training as well as persistence of changes 12 weeks after the end of the training programs. To address aim 3, validated questionnaires will be used to examine changes in anxiety and perceived stress symptoms and condition-specific quality of life over 12 weeks of yoga or stretching training as well as persistence of changes 12 weeks after the end of the training programs.

### **4. SELECTION AND ENROLLMENT OF PARTICIPANTS**

Eligibility criteria have designed to identify a population that is generalizable to most ambulatory middle-aged and older women with incontinence in the community who do not have a major contraindication to practicing yoga.

#### **4.1 Inclusion Criteria**

Candidates must meet all of the following criteria to participate in the study:

- Women aged 50 years or older who report urinary incontinence starting at least 3 months prior to screening
- Self-report at least 3 urinary incontinence episodes on a screening 3-day voiding diary (i.e., an average of at least one episode per day)
- Self-report urgency-predominant (i.e., at least half of incontinence episodes being urgency-type), stress-predominant (i.e., at least half of episodes being stress-type), or mixed-type (i.e., an equal number of stress- and urgency-type episodes) incontinence on the screening voiding diary
- Willing to refrain from initiating medical treatments that may affect their incontinence or voiding pattern during the study intervention period

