## **5.4 Adherence Assessment**

Adherence to group yoga and physical conditioning classes will be documented by the study class instructors using standardized attendance logs. Attendance logs will be returned to clinical coordinators on at least a weekly basis throughout the yoga therapy and physical conditioning programs. Clinical coordinators will immediately contact any participant who misses a scheduled class to ask about reasons for missing the class, reinforce the importance of class attendance, and troubleshoot any barriers to attendance.

Adherence to home practice of yoga or stretching/strengthening exercises will be tracked using home practice logs. Participants will be instructed to record the date, time, and duration of each home practice session in their logs, as well as the specific yoga poses or stretching/strengthening exercises practiced during each session. Home practice logs will be collected by class instructors and returned to the clinical coordinators on a weekly basis during the 12-week treatment program. Clinical coordinators will contact any participant whose log indicates that she is not practicing yoga or stretching exercises at least one hour a week at home. Additionally, home practice logs will be returned by mail 12 weeks after the end of the intervention program to assess home practice during the post-treatment follow-up period.

Every effort will be made to encourage participants to complete all intervention classes and practice sessions. Prior to randomization, study coordinators will stress the importance of adherence to group classes and home practice, and only those women who indicate that they are available on scheduled class dates and willing to practice yoga or stretching exercises at home as recommended will be eligible for randomization. The importance of adherence will again be stressed at the orientation session for each yoga or physical conditioning series, as well as during follow-up telephone calls 2 weeks and follow-up visits at 8 weeks. Additionally, attendance sheets from yoga and stretching classes will be carefully monitored, and home practice logs will be reviewed weekly, so that study staff can immediately call any women who miss classes or fail to document home practice in order to reinforce the importance of attendance/practice and troubleshoot barriers to adherence.

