#### **6.2.4 Randomization and Blinding**

##### Randomization

Women who are confirmed to be eligible and available to take part in upcoming yoga or physical conditioning group class series will be randomized in a 1:1 ratio to one of the two intervention groups. Randomization will ideally take place within 1 month of completion of screening procedures, and in no cases will be able to take place more than 2 months after completion of screening procedures. Randomization must also take place within 2 weeks of the start of yoga or physical conditioning class series. If the Baseline Clinic Visit occurs within 2 weeks of the start of the yoga therapy or physical conditioning program, eligible participants will be randomized to one of the two interventions directly at this visit. If the Baseline Clinic Visit occurs more than 2 weeks before the start of the intervention program, eligible participants will be scheduled for a Randomization Telephone Call within two weeks of the start of the program to determine their intervention assignment.

During the Baseline Clinic visit or during the Randomization Telephone Call

(whichever is appropriate), randomization will be performed according to a pre-established computer-algorithm using randomly permuted blocks of sizes 2 and 4 (limited block size to ensure that the number of randomized participants within each strata always exceeds the block size).

Randomization will be stratified by clinical type of incontinence (i.e., stress, urgency, or mixed) to ensure adequacy of randomization among women with each major incontinence type. Randomization will be implemented. Prior to randomization, the research coordinator will complete a randomization checklist confirming that the participant meets all eligibility criteria.

Additionally, participants' availability and willingness to attend upcoming yoga or physical conditioning group classes will be re-confirmed before randomization assignment is obtained.

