Standard allocation concealment procedures will be followed to avoid manipulation of randomization. Prior to the start of recruitment, the randomization scheme will be developed by a statistical programmer who will have no contact with participants or role in data entry, cleaning, or analysis. To execute the randomization scheme, a research assistant who will also have no contact with participants or access to study data will then prepare a series of sealed, opaque envelopes containing group assignment, numbered consecutively with the randomization sequence numbers. When the participant is ready for randomization, study coordinators will enter the date, participant name, and study ID in the randomization log and select the next numbered envelope corresponding to the participants' type of incontinence (stress-, urgency-, or mixed-type) to determine group assignment. Once a participant has been randomized, she cannot be re-assigned to a different intervention group. All randomization envelopes will be retained for review; randomization dates and times should follow the order of the sequence numbers, providing a check on validity.

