#### Blinding

Although participants cannot be blinded to treatment assignment (due to the behavioral nature of the intervention), study procedures have been carefully designed to avoid bias associated with knowledge of group assignment. First, to minimize differential expectations of treatment success, participants will be told that they are participating in a study of two different types of low-impact group activity-based interventions to enhance self-management of incontinence, and that we do not know which is more effective (which is true). The primary outcome will be assessed by voiding diaries, a measure that is resistant to reporting bias, and data from returned diaries will be abstracted by blinded analysts. Similarly, data from participant follow-up questionnaires assessing other symptom and quality-of-life outcomes associated with incontinence will be abstracted by blinded analysts.

Only study personnel who are involved in delivering the therapeutic interventions, assessing and promoting adherence to these interventions, and/or monitoring adverse events related to these interventions will be aware of group assignment. All investigators, study analysts involved in abstracting efficacy outcomes data, and statistical programmers involved in ongoing data cleaning will be blinded to treatment allocation. Unless stipulated by the Data and Safety Monitor or required to assist with the clinical management of a participant experiencing a serious adverse event, these investigators and

staff will remain blinded until after all participants have completed their final visit, trial data are edited and cleaned, and the trial dataset is locked. A statistical programmer who is not involved in data collection or cleaning will be appointed to create the unblinded group-specific data tables for closed session Data and Safety Monitor reviews.

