## 7.2 Methods and Timing of Safety Assessments

To monitor participant safety, a clinical coordinator will assess for adverse events at each follow-up telephone and in-person contact following randomization, starting with the 2-Week Telephone Call. Negative changes in health will be recorded as adverse events or serious adverse events on standardized forms as appropriate (see sections 7.3 and 7.4 below for definitions and documentation). Additionally, if participants contact clinical coordinators in between scheduled study visits and calls and report negative changes in their health, these will also be recorded as adverse events or serious adverse events.

Coordinators will not prompt participants to provide information about specific types of adverse events at follow-up visits, but instead encourage participants to volunteer information by asking the standardized, open-ended question, "Have there been any changes in your health since your last visit?" Any negative changes in health reported by participants will then be recorded on standardized AE or SAE forms, as appropriate (see section 7.3 below).

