## 10. DATA COLLECTION AND QUALITY ASSURANCE

### 10.1 Data Collection Forms

Study data will be obtained from participant-completed symptom diaries and logs, participant- or interviewer-administered questionnaires, physical examination and performance measures, and urine sampling/testing. Forms for recording or abstracting data will be developed specifically for this study, including:

- Voiding diary abstraction form: After participants complete their 3-day voiding diary at home, they will return the completed diary to the study clinic, and diary data will be abstracted using a Voiding Diary Abstraction Form. At the Baseline Visit, a clinical coordinator will abstract diary data for eligibility assessment purposes; at all post-randomization follow-up assessments, an analyst who is blinded to intervention assignment will abstract diary data.
- Questionnaires assessing anxiety and perceived stress, condition-specific quality of life, and participant satisfaction: These questionnaire forms will be completed by the participant during clinic visits and returned in person to a clinical coordinator, or completed by the participant at home and then mailed back to the study clinic (in the case of the 12 week post-treatment assessment). Questionnaire data collected after randomization will be entered into the electronic database by an analyst who is blinded to intervention assignment.
- Questionnaires assessing demographic history, general medical and urologic/urogynecologic history, medication use, tobacco and alcohol use, and physical activity and function: These questionnaires will be administered by a clinical coordinator during in-person study visits, and data from questionnaires will subsequently be entered by the coordinator into the electronic database. Because these data will not be used to assess efficacy outcomes, the coordinators who administer and enter data from these forms will not necessarily be blinded to intervention assignment.

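### Do the overlapping incontinence-type definitions in section 4.1 leave the randomization stratum undefined for women with equal stress and urgency counts?

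*Combined protocol and SAP*

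**What the plan says.** Section 4.1 admits women whose screening diary shows at least 3 episodes and whose incontinence is "urgency-predominant (i.e., at least half of incontinence episodes being urgency-type), stress-predominant (i.e., at least half of episodes being stress-type"), or mixed, meaning "an equal number of stress- and urgency-type episodes". Section 6.1.1 has the participant classify each episode as urgency, stress or other, so a diary yields three counts.

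The same three labels serve as strata. Section 6.2.4 states: "Randomization will be stratified by clinical type of incontinence (i.e., stress, urgency, or mixed"). Sections 4.3 and 9.3 repeat this. Blocks are of size 2 and 4. In 6.2.4 coordinators "select the next numbered envelope corresponding to" the participant's type. Section 9.3 says type is confirmed before the envelope is drawn, but its envelope sentence does not repeat that the series follows type.

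On who does the work, section 10.1 says: "At the Baseline Visit, a clinical coordinator will abstract diary data for eligibility assessment purposes". Coordinators also deal with attendance (5.4: "Clinical coordinators will immediately contact any participant who misses a scheduled class") and safety (7.2: "a clinical coordinator will assess for adverse events at each follow-up telephone and in-person contact following randomization"). Under the Blinding heading of 6.2.4, staff involved in "assessing and promoting adherence to these interventions, and/or monitoring adverse events related to these interventions will be aware of group assignment".

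No section gives an order of precedence among the three types.

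**The concern.** Both predominant definitions are inclusive, so a woman whose episodes split exactly in half is urgency-predominant, stress-predominant and mixed at once. For eligibility this is harmless. For stratified randomization it matters in principle, because the label selects the envelope series and three labels offer three series.

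The person resolving the tie may be a coordinator who abstracts the baseline diary, draws the envelope and knows the assignments of women already in classes. With blocks of 2 and 4, known earlier assignments say something about the next one. A free choice of series could therefore become an opening for selection bias. The plan's own validity check is that dates and times follow the sequence numbers. It would not reveal such a choice, because the next envelope in any of the three series is in order.

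**Working it through.** **1. Where the definitions overlap.** Let u, s and o be the urgency, stress and other counts, with n = u + s + o and n at least 3. Section 4.1, read literally, gives:

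- urgency-predominant if 2u ≥ n
- stress-predominant if 2s ≥ n
- mixed if u = s

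If both predominant conditions hold, adding them gives u + s ≥ n. Since u + s = n − o, this forces o = 0 and u = s = n/2, and then mixed holds as well. So the only multiple label is the triple one, and it needs an even total of at least 4 with no other-type episode. If u = s and o > 0, each type is below half and only mixed applies.

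**2. Count of patterns, 3 to 10 episodes.** For total n there are (n + 1)(n + 2)/2 patterns: 10 + 15 + 21 + 28 + 36 + 45 + 55 + 66 = 276.

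| Labels returned | Mixed requires at least one of each type | Section 4.1 strictly literal |
|---|---|---|
| All three | 4 | 4 |
| Exactly one | 184 | 192 |
| None | 88 | 80 |

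The 4 are 2/2/0, 3/3/0, 4/4/0 and 5/5/0 (stress/urgency/other). The 184 are 82 urgency, 82 stress and 20 mixed. The columns differ by 8, one all-other diary per total, because 0 = 0 literally counts as equal. Sections 3, 4.3 and 6.2.3 require stress, urgency or mixed incontinence, so the middle column is the sensible reading. These are patterns, not women; the documents give no frequency for ties.

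**3. Evident meaning.** If exact ties without other-type episodes were not mixed, the mixed stratum would hold only women who also had other-type episodes: the 20 patterns above and none of the 4. That is an implausible design. Classing equal counts as mixed gives every eligible pattern exactly one label, changes eligibility for none and relabels none of the 184.

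**4. Effect of an inconsistent label without steering.** If the choice of label does not depend on what the next envelope holds, the chance of yoga is 1/2 in each series, so it is 1/2 whichever series is used. The comparison stays unbiased. The section 9.8 model uses treatment group, week and the baseline value and does not list stratum, so the label does not enter the analysis.

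**5. Worst case with steering.** Assumptions: the coordinator knows every earlier assignment in all three series, knows the blocking scheme, may use any of the three, and wants a particular arm. Block sizes 2 and 4 are taken as equally likely, which the documents do not state. The probability of the wanted arm is the largest of three posterior probabilities for the next assignment. Simulation with 0–29, 5–29 or 1–10 earlier assignments per series gives 0.742, 0.753 and 0.746; a repeat run gave 0.745, 0.750 and 0.745. With the series fixed by rule it is 0.50.

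For scale, with 90 women and an assumed tied share t, the expected number moved to the wanted arm is at most about 90 × t × (0.75 − 0.50):

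- t = 5%: 1.1
- t = 10%: 2.3
- t = 20%: 4.5

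Much of this predictability comes from the small blocks rather than the tie. Under the same assumptions, a coordinator confined to one series already guesses the next assignment correctly about 72% of the time.

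**The case for a change.** The best case for a change is that allocation is the step the plan takes most care to protect, and the written rule returns three answers for some women. Sealed, opaque envelopes hide their contents but do not fix which series is opened, and the sequence check is blind to that choice. The trial exists to develop procedures for a larger one, so loose wording could carry over. The remedy costs one sentence.

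Several of these points stand. The literal overlap is there, no tie-break is written, and the sequence check would not catch a switched series. What does not stand is the step from there to a defect in the allocation:

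- The clause for equal counts names them mixed, and the word predominant does not naturally describe a type that only equals its rival.
- A working rule may sit on the diary abstraction form (10.1) or the randomization checklist (6.2.4). Neither form is in the documents, so its absence cannot be shown.
- Section 10.3.2 has diary abstraction forms verified against source by someone who did not enter the data. The counts behind a label can therefore be audited afterwards, though this supplies no tie-break.
- The shorter envelope sentence in 9.3 contradicts nothing in 6.2.4. The same section states that randomization is stratified by type and that type is confirmed first.

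Low cost alone is a reason for optional tidying, not for a required change.

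**Conclusion.** No change to the plan is needed. This is an unwritten tie-break that staff would fill as mixed, and following the plan as it stands still gives a sound allocation.

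The ambiguity is confined to diaries with equal stress and urgency counts and no other-type episodes. It changes no eligibility decision, reading all-other diaries as ineligible. It changes no estimate specified in section 9.8, and the trial is by its own account an unpowered pilot (9.1, 9.2). The figure of about 0.75 against 0.50 is a theoretical ceiling that needs full knowledge of three series and intent to steer; it is not evidence of likely harm. How many women it could touch is unknown.

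The conclusion rests on two assumptions: that coordinators read equal counts as mixed, and that any stray label is not chosen with an eye to the next envelope. If the wording is reused for the full-scale trial, stating the tie rule there would be a reasonable courtesy to site staff.
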